5. STUDY POPULATION

5.1. Number of Subjects

This study will enroll 16 healthy subjects both male and female, aged 18-60 years, at the pharmacokinetic unit Faculty of Tropical Medicine, Mahidol University. Subjects will be healthy HIV-1, hepatitis B and C uninfected individuals who comprehend the purpose of the study and have provided written consent. All subjects will undergo screening assessments (visit 1). Screening assessments (visit 1) may be carried out over more than one day, provided that all required assessments are completed within the 14 days prior to visit 2. If the interval between screening (visit 1) and day -1 visit 2 is three days or less, the clinical laboratory screening test result and serum pregnancy test result can be used for enrolment evaluation on day -1 visit 2. In such cases, these tests would not need to be repeated at day-1 visit 2.

5.2. Inclusion Criteria

In order to be eligible to enter the protocol, subjects must meet the following criteria:

- 1. Healthy as judged by a responsible physician with no abnormality identified on a medical evaluation including medical history and physical examination.
- 2. Male or female non-smoker aged between 18 years to 60 years.
- 3. A female is eligible to enter and participate in this study if she is:
 - of non-childbearing potential including pre-menopausal females with documented (medical report verification) hysterectomy or double oophorectomy
 - or postmenopausal defined as 12 months of spontaneous amenorrhea or 6 months of spontaneous amenorrhea with serum follicle stimulating hormone levels >40 mIU/mL or 6 weeks postsurgical bilateral oophorectomy with or without hysterectomy
 - or of childbearing potential, has a negative serum pregnancy test at screening and prior to start the study drug in each period, and agrees to abstain from sexual intercourse or use effective contraceptive methods (e.g., intrauterine device, hormonal contraceptive drug, tubal ligation or female barrier method with spermicide) during the study until completion of the follow-up procedures
- 4. A male is eligible to enter and participate in this study if he: agrees to abstain from sexual intercourse with females of childbearing potential or lactating females; or is willing to use a condom/spermicide, during the study until completion of the follow-up procedures.

- 5. Normal electrocardiogram (ECG) with QTc <450 msec.
- 6. Willingness and ability to comply with the study protocol for the duration of the trial.

5.3. Exclusion Criteria

Subjects will not be enrolled into the study if they meet any of the following exclusion criteria:

- 1. Females who are pregnant, trying to get pregnant, or are lactating.
- 2. The subject has evidence of active substance abuse that may compromise safety, pharmacokinetics, or ability to adhere with protocol instructions.
- 3. A positive pre-study hepatitis B surface antigen, positive hepatitis C antibody, or positive human immunodeficiency virus-1 (HIV-1) antibody result at screening.
- 4. Subjects with a personal history of cardiac disease, symptomatic or asymptomatic arrhythmias, syncopal episodes, or additional risk factors for torsades de pointes (heart failure, hypokalemia) or with a family history of long QT syndrome, Brugada syndrome, or sudden cardiac death.
- 5. Abnormal serum creatinine (Scr) and estimated glomerular filtration rate (eGFR) <70 mL/min as determined by CKD-EPI equation
- 6. History of alcohol or substance abuse or dependence within 6 months of the study.
- 7. Use of prescription or non-prescription drugs except paracetamol at doses of up to 2 grams/day, including vitamins, herbal and dietary supplements (including St. John's Wort) within 7 days (or 14 days if the drug is a potential enzyme inducer) or 5 times the drug half-life (whichever is longer) prior to the first dose of study medication until the completion of the follow-up procedure, unless in the opinion of investigator, the medication will not interfere with the study procedures or compromise subject safety; the investigator will take advice from the manufacturer representative as necessary.
- 8. The subject has participated in a clinical trial and has received a drug or a new chemical entity within 30 days or 5 x half-life, or twice the duration of the biological effect of any drug (whichever is longer) prior to the first dose of study medication.
- 9. The subject is unwilling to abstain from ingesting alcohol within 48 hours prior to the first dose of study medication until collection of the final pharmacokinetic sample during each regimen.
- 10. Subjects who have donated blood to the extent that participation in the study would result in more than 300 mL blood donated within a 30-day period. Note: This does not include plasma donation.
- 11. Subjects who have a history of allergy to the study drug or drugs of this class, or a history of drug or other allergy that, in the opinion of the investigator, contraindicates participation in the trial. In addition, if heparin is used during pharmacokinetic sampling, subjects with a history of sensitivity to heparin or heparin-induced thrombocytopenia should not be enrolled.
- 12. Lack of suitability for participation in this study, including but not limited to, unstable medical conditions, systemic disease manifested by tendency to granulocytopenia e.g. rheumatoid arthritis and lupus erythematosus that in the opinion of the investigator would compromise their participation in the trial.

- 13. AST or ALT >1.5 times the upper limit of normal (ULN)
- 14. Subjects with history of renal disease, hepatic disease, and/or cholecystectomy
- 15. Abnormal methemoglobin level (more than 3 mg/dL).
- 16. History of antimalarial drugs use including but not limited to mefloquine, chloroquine, primaquine, artesunate, piperaquine and pyronaridine treatment within 6 months.
- 17. Subject who have received quinacrine in last 30 days.
- 18. Subject has been included in other clinical trials in last 6 months.

6. STUDY ASSESSMENTS AND PROCEDURES

Each subject will have adequate time to provide informed consent of his or her own free will and prior to conducting any study specific procedures. Each subject will be provided a copy of the signed informed consent prior to the initiation of any study procedures.

After a subject has provided written informed consent, the investigator or other study personnel will determine if the subject is eligible for enrolment in the study. This will be done by reviewing the inclusion and exclusion criteria and completing all of the screening assessments.

The pharmacokinetic blood samples for a subject should be obtained at the scheduled times relative to when the subject was dosed.

6.1 Study Procedures (Appendix 2)

6.1.1 Visit 1 (Screening visit)

Subjects will be screened to assess eligibility. Full consent will be obtained before any screening procedures are conducted.

- Basic demographics including age, date of birth, sex, height, and body weight
- Physical Examination and symptoms questionnaire assessment
- Vital signs (blood pressure (BP), respiratory rate (RR), body temperature (BT) and heart rate (HR)) and medical history
- ECG
- Clinical laboratory assessment:
 - o chemistry: Albumin, ALP, ALT, AST, total and direct bilirubin, BUN, creatinine, creatine kinase, potassium, sodium, magnesium and calcium
 - o hematology: hemoglobin, hematocrit, white blood cell count with differential and platelet count
 - o fasting blood sugar (FBS) (at screening and during admission)
 - o urinalysis: white blood cell, red blood cell and protein
 - o *TSH (at screening visit only)
 - o HIV antibody, hepatitis B surface antigens, and hepatitis C antibody tests. (Pre and Post-test counseling will be performed for HIV test) (These tests

will be done at screening visit only)

Note: The remaining serum will be frozen and stored for use in an exploratory analysis evaluating independent renal markers against standard blood urea nitrogen/ creatinine levels as markers of renal toxicity.

All laboratory assessments (chemistry, hematology, FBS and urinalysis) must be drawn in the fasting state (8 hours fast). Blood collection for clinical laboratory assessment is approximately 10 mL.

• Serum pregnancy testing (if appropriate)

6.1.2 Visit 2-4

16 healthy subjects who fulfill the eligibility criteria will be recruited and randomized to the study.

Procedures on each admission (Appendix 2):

Visit 2

Day -1 (admission)

- Physical Examination and symptoms questionnaire assessment
- Chemistry, Hematology, FBS and urinalysis assessment
- 24-hour urine for creatinine clearance test
- Genetic sample collection (Genetic sample can be collected at any of the subsequent days or visits, if it is missed today)
- Vital signs will be checked every 4 hours.
- ECG monitoring according to table 2
- Holter monitoring (~30 mins baseline recording)
- Urine pregnancy test (if applicable)

Day 0-3 (admission)

- Daily physical examination and symptoms questionnaire assessment
- Vital signs will be checked before and every 4 hours after first dose.
- ECG monitoring according to table 2
- Continuous Holter monitoring during admission.
- Pharmacokinetic samples will be collected according to table 2
- Study drug administration (Artemether-lumefantrine OR Amodiaquine) will be given according to table 1.
- 24-hour urine for creatinine clearance test (Day 2)
- Chemistry, Hematology, FBS and urinalysis assessment before discharge

Day 4 (+1) (follow up)

• Physical Examination, vital signs and symptoms questionnaire assessment

- Pharmacokinetic sample collection
- ECG

Day 7 (+/-2d) (follow up)

- Physical Examination, vital signs and symptoms questionnaire assessment
- Chemistry, Hematology and urinalysis assessment
- Pharmacokinetic sample collection
- ECG
- Holter monitoring (~ 30 mins)

Day 14 (+/-2d) (follow up)

- Physical Examination, vital signs and symptoms questionnaire assessment
- Chemistry, Hematology and urinalysis assessment
- Urine pregnancy test (if applicable)
- Pharmacokinetic sample collection
- ECG

Day 21 (+/-2d) (follow up)

- Physical Examination, vital signs and symptoms questionnaire assessment
- Chemistry, Hematology and urinalysis assessment
- ECG

Day 28 (+/-2d) (follow up)

- Physical Examination, vital signs and symptoms questionnaire assessment
- Chemistry, Hematology and urinalysis assessment
- Urine pregnancy test (if applicable)
- Pharmacokinetic sample collection
- ECG
- Holter monitoring (~ 30 mins)

Day 35 (+/-2d) (follow up) (for Amodiaquine only)

- Physical Examination, vital signs and symptoms questionnaire assessment
- Chemistry, Hematology and urinalysis assessment
- ECG

Day 42 (+/-2d) (follow up) (for Amodiaquine only)

- Physical Examination, vital signs and symptoms questionnaire assessment
- Chemistry, Hematology and urinalysis assessment
- Urine pregnancy test (if applicable)
- Pharmacokinetic sample collection

• ECG

Visit 3

Day -1 (admission)

- Physical Examination and symptoms questionnaire assessment
- Chemistry, Hematology, FBS and urinalysis assessment
- 24-hour urine for creatinine clearance test
- Vital signs will be checked every 4 hours.
- ECG monitoring according to table 2
- Holter monitoring (~30 mins baseline recording)
- Urine pregnancy test (if applicable)

Day 0-3 (admission)

- Daily physical examination and symptoms questionnaire assessment
- Vital signs will be checked before and every 4 hours after first dose.
- ECG monitoring according to table 2
- Continuous Holter monitoring during admission.
- Pharmacokinetic samples will be collected according to table 2
- Study drug administration (Amodiaquine OR Artemether-lumefantrine) will be given according to table 1.
- 24-hour urine for creatinine clearance test (Day 2)
- Chemistry, Hematology, FBS and urinalysis assessment before discharge

Day 4 (+1) (follow up)

- Physical Examination, vital sign and symptoms questionnaire assessment
- Pharmacokinetic sample collection
- ECG

Day 7 (+/-2d) (follow up)

- Physical Examination, vital signs and symptoms questionnaire assessment
- Chemistry, Hematology and urinalysis assessment
- Pharmacokinetic sample collection
- Holter monitoring (~ 30 mins)
- ECG

Day 14 (+/-2d) (follow up)

- Physical Examination, vital signs and symptoms questionnaire assessment
- Chemistry, Hematology and urinalysis assessment
- Urine pregnancy test (if applicable)

- Pharmacokinetic sample collection
- ECG

Day 21 (+/-2d) (follow up)

- Physical Examination, vital signs and symptoms questionnaire assessment
- Chemistry, Hematology and urinalysis assessment
- ECG

Day 28 (+/-2d) (follow up)

- Physical Examination, vital signs and symptoms questionnaire assessment
- Chemistry, Hematology and urinalysis assessment
- Urine pregnancy test_(if applicable)
- Pharmacokinetic sample collection
- Holter monitoring (~ 30 mins)
- ECG

Day 35 (+/-2d) (follow up) (for Amodiaquine only)

- Physical Examination, vital signs and symptoms questionnaire assessment
- Chemistry, Hematology and urinalysis assessment
- ECG

Day 42 (+/-2d) (follow up) (for Amodiaquine only)

- Physical Examination, vital signs and symptoms questionnaire assessment
- Chemistry, Hematology and urinalysis assessment
- Urine pregnancy test (if applicable)
- Pharmacokinetic sample collection
- ECG

Visit 4

Day -1 (admission)

- Physical Examination and symptoms questionnaire assessment
- Chemistry, Hematology, FBS and urinalysis assessment
- 24-hour urine for creatinine clearance test
- Vital signs will be checked every 4 hours.
- ECG monitoring according to table 2
- Holter monitoring (~30 mins baseline recording)
- Urine pregnancy test (if applicable)

Day 0-3 (admission)

- Daily physical examination and symptoms questionnaire assessment
- Vital signs will be checked before and every 4 hours after first dose.
- ECG monitoring according to table 2
- Continuous Holter monitoring during admission.
- Pharmacokinetic samples will be collected according to table 2
- Study drug administration (Artemether-lumefantrine AND Amodiaquine) will be given according to table 1.
- 24-hour urine for creatinine clearance test (Day 2)
- Chemistry, Hematology, FBS and urinalysis assessment before discharge

Day 4 (+1) (follow up)

- Physical Examination, vital signs and symptoms questionnaire assessment
- Pharmacokinetic sample collection
- ECG

Day 7 (+/-2d) (follow up)

- Physical Examination, vital sign and symptoms questionnaire assessment
- Chemistry, Hematology and urinalysis assessment
- Pharmacokinetic sample collection
- ECG
- Holter monitoring (~ 30 mins)

Day 14 (+/-2d) (follow up)

- Physical Examination, vital signs and symptoms questionnaire assessment
- Chemistry, Hematology and urinalysis assessment
- Urine pregnancy test (if applicable)
- Pharmacokinetic sample collection
- ECG

Day 21 (+/-2d) (follow up)

- Physical Examination, vital signs and symptoms questionnaire assessment
- Chemistry, Hematology and urinalysis assessment
- ECG

Day 28 (+/-2d) (follow up)

- Physical Examination, vital signs and symptoms questionnaire assessment
- Chemistry, Hematology and urinalysis assessment
- Urine pregnancy test_(if applicable)
- Pharmacokinetic sample collection

- ECG
- Holter monitoring (~ 30 mins)

Day 35 (+/-2d) (follow up)

- Physical Examination, vital signs and symptoms questionnaire assessment
- Chemistry, Hematology and urinalysis assessment
- ECG

Day 42 (+/-2d) (follow up)

- Physical Examination, vital signs and symptoms questionnaire assessment
- Chemistry, Hematology and urinalysis assessment
- Urine pregnancy test (if applicable)
- Pharmacokinetic sample collection
- ECG

All laboratory assessments (chemistry, hematology, FBS and urinalysis) must be drawn in the fasting state (8 hours fast). Results of these tests are to be available and reviewed prior to each subject receiving the study drug on day 0.

Note: At all visits the remaining blood serum will be frozen and stored for use in an exploratory analysis evaluating independent renal markers against standard blood urea nitrogen/ creatinine levels as markers of renal toxicity.

6.3 Safety Assessments

The physician or qualified clinical study staff will review the data at intervals throughout each study period.

6.3.1. Adverse Events

Adverse events (AEs) and serious adverse events (SAEs) will be monitored. Refer to Section on AEs and SAEs.

6.3.2. Vital Signs (BP, RR, BT and HR)

Subjects must have been resting quietly for at least 10 minutes prior to taking measurements.

Blood pressure (BP) and heart rate (HR) for visit 2-4 will be measured in both supine standing position in each time-points.

6.3.3. ECGs

Subjects must have been resting quietly for at least 20 minutes prior to taking measurements. Each ECG measurement will be done in triplicate at each time point to avoid outlier values due to random variation.

6.3.4 Holter monitor

During each admission, subjects will undergo continuous Holter monitoring to record changes in heart rhythm and cardiac conduction times. Simple non-invasive autonomic function tests i.e. heart-rate response to postural change (further detailed in an SOP) will be undertaken during the time that the Holter monitor is fitted (including during follow-up if a Holter monitor is available).

6.3.5. Clinical Laboratory Assessments

The following hematology, clinical chemistry, FBS, and urinalysis tests will be performed at each admission.

- Hematology: hemoglobin, hematocrit, white blood cell (WBC) count with differential, and platelet count
- Chemistry: Albumin, alkaline phosphatase (ALP), alanine aminotransferase (ALT), aspartate aminotransferase (AST), total and direct bilirubin, blood urea nitrogen (BUN), creatinine, creatine kinase (CK), potassium, sodium, magnesium and calcium
- FBS: Fasting blood sugar (at screening and during admission)
- Urinalysis: white blood cell (WBC), red blood cell count (RBC), and protein.
- *TSH (for screening visit only)

Note: The remaining blood serum will be frozen and stored for use in an exploratory analysis evaluating independent renal markers against standard blood urea nitrogen/ creatinine levels as markers of renal toxicity.

Any results falling outside of the reference range will be repeated at the discretion of the investigator. If there is more than one laboratory result for the same analyte, the last value will be recorded in the CRF.

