10.3 Subject discontinues the study drugs

Such subjects will be followed up for safety data collection. Reasons for this scenario may include:

- Pregnancy
- Subject requests to discontinue study drugs
- Abnormal renal and hepatic laboratory result including;
 - o Any creatinine above 1.5 x ULN OR increase 0.3 mg/dL above baseline
 - o Any ALT or AST above 3 x ULN
 - o Any elevation in total and direct bilirubin 2x ULN
 - o Any AST or ALT above 2xULN and TBL >1.5xULN

o Any AST or ALT above 2xULN with the appearance of fatigue, nausea, vomiting, right upper quadrant pain or tenderness, fever, rash and/or eosinophilia (eosinophil percent or count above the ULN)

If the abnormalities are potentially caused by one of the study drug the research physician will decide whether the other regimen of the study drugs should be continued. All laboratory abnormalities will be assessed by a trained physician. In case of abnormalities, a medical history to assess exposure to substances (medication, alcohol and others) with known toxicity for instance liver or kidney will be performed. In addition, the physician can perform additional investigations that are deemed necessary to explain the laboratory abnormalities (such as hepatitis serology or urine analysis). The liver function and creatinine abnormalities will be monitored until resolution or the stabilization of the condition. In any case all laboratory values should have returned to normal (within the normal range in the case of full blood count values and at least <1.5 times the ULN in case of the biochemistry values) before the administration of the next treatment round.

- QTc interval abnormalities;
- QTc or QT interval longer than 500 milliseconds

A case by case judgement will be made on whether the subjects should be discontinued from the study completely. All other drugs known to prolong the QTc interval will be stopped. QTc intervals will be monitored continuously until normalisation of the QTc interval to below 450 milliseconds. Magnesium and potassium levels will be measured and deficiencies will be supplemented through intravenous or oral medication.

Unevaluable subjects may be replaced, according to the discretion of the investigators with another subject of the same population, if either sample size or completeness of dataset is compromised. All data will be listed and will be valid for clinical safety and tolerability evaluation.

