12.5.2 Safety Analysis

Safety analyses will be based on the safety set. Safety and tolerability of artemether, lumefantrine and amodiaquine will be assessed by comparing the frequency (%) of adverse events and serious adverse events, with particular attention to abdominal pain, appetite perturbation and QT interval prolongation, using the Fisher's exact test. Safety data will be presented in tabular and/or graphical format and summarized descriptively. Any clinically relevant abnormalities or values of potential clinically concern will be described. Subjects will be analysed as treated.

An additional exploratory analysis evaluating independent renal markers against standard blood urea nitrogen/ creatinine levels will be conducted using appropriate statistical methods.

Adverse Events

All adverse event summaries will refer to treatment emergent adverse events, i.e. adverse

events that newly started or increased in intensity after the study drug administration. AE summaries will be generated for all AEs that occurred after study drug administration, until the end of the study.

12.6 Assessment of the relationship between pharmacokinetic parameters and ECG findings.

In addition to the results of the safety analysis, an exploratory analysis of the ECG data will be conducted. The ECG parameters will be compared with the PK properties of the drugs using appropriate statistical methods.

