13.6. Data Management

The data collection tool for this study will be approved case report forms (CRFs). Subject data necessary for analysis and reporting will be entered/transmitted into a validated database or data system. Clinical data management will be performed in accordance with applicable standards and data cleaning procedures.

Study records will be stored for a period of 10 years after completion of the study, while electronic data will be retained indefinitely.

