13.7. Study Monitoring

The trial will be conducted in compliance with this protocol, International Conference on Harmonization (ICH) Guidelines for Good Clinical Practice (GCP) and any applicable regulatory requirement(s). Monitors will visit the clinical research sites to monitor all aspects of the study in accordance with the appropriate regulations. The objectives of a monitoring visit will be:

1) to verify the prompt reporting of all data points, including reporting SAEs, checking availability of signed informed consent

2) to compare individual subject records and the source documents (supporting data, laboratory specimen records and medical records to include physician progress notes, nurses' notes, subjects' hospital charts)

3) to ensure protection of study subjects, compliance with the protocol, and accuracy and completeness of records

The monitors will be involved with the site initiation visit, study close out visit and interim monitoring visits the number of which will be determined by the quality of the site. In addition, the monitor will inspect the clinical sites regulatory files to ensure that regulatory requirements are being followed. During the monitoring visits, the investigator (and/or designee) and other

study personnel will be available to discuss the study progress and monitoring visit.

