3. ANALYSIS**3.1 GENERAL CONSIDERATIONS**

The main strategy of analysis will be characterising the potential pharmacokinetic interactions of artemether - lumefantrine and amodiaquine . Safety analysis will also be done for potential signals and clinical importance. Means (SD) will be used to summarise normally distributed baseline variables. Non-normally distributed variables will be summarised using medians (IQR). Count data will be summarised using frequency counts and percentages. The percentages/proportions will be compared using Fisher's Exact test and a significance level of 5%. Detailed analysis approaches are provided in the relevant sections below.

STATISTICAL ANALYSIS PLAN FOR ALAQ STUDY

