3.5.3 Safety assessments

The incidence of AEs will be tabulated and reviewed for potential signals and clinical importance. The most prevalent AEs will be reported by group: (AL → AQ → AL + AQ) vs (AQ → AL → AL + AQ). Any Serious Adverse Events (SAEs) including any deaths will also be reported by group. Standard haematological parameters, serum chemistries, liver and renal function test results at screening and post-treatment will be summarised across the treatment groups. For the safety data such as adverse events, proportions will be compared using Fisher's exact test and a significance level of 5% where appropriate.

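### Discretionary repeats of out-of-range laboratory results, with the last value recorded, let first abnormal values be selectively replaced in the safety summaries (minor)

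*Protocol*

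**What the plan says.** Protocol 6.3.5 contains two linked sentences. The first sets the trigger: "Any results falling outside of the reference range will be repeated at the discretion of the investigator". The second sets the recording rule: "If there is more than one laboratory result for the same analyte, the last value will be recorded in the CRF". The section gives no interval within which a further result counts as a repeat of a scheduled one, and no instruction to keep the earlier value.

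Protocol 13.6 makes the case report form (CRF) the data collection tool. Protocol 3.2 lists biochemical assessments within a secondary safety endpoint. SAP 3.5.3 then plans: "Standard haematological parameters, serum chemistries, liver and renal function test results at screening and post-treatment will be summarised across the treatment groups". It has no provision for repeat or unscheduled results.

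Other sections also deal with abnormal results:

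- Protocol 11.1 and 11.2 treat abnormal laboratory findings as adverse events.
- Protocol 10.3 lists renal and hepatic limits, and adds: "The liver function and creatinine abnormalities will be monitored until resolution or the stabilization of the condition".
- Protocol 12.5.2 says: "Any clinically relevant abnormalities or values of potential clinically concern will be described".
- Protocol 13.7 has monitors check subject records against source documents, including laboratory specimen records.

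**The concern.** The retest is triggered by the result itself. A value just outside the reference range may be drawn again and replaced. A value just inside it stays. A high first value is partly chance, so the repeat tends to lie closer to the subject's usual level, and the recorded data are trimmed on the abnormal side. The choice of which results to repeat belongs to an investigator who knows the regimen, because the trial is open-label (Protocol 4).

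The missing time point adds to this. Monitoring under Protocol 10.3 produces further values of the same analyte. Read literally, the last-value rule could put a recovered value in the place of the scheduled one.

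At stake are the descriptive laboratory summaries that support a secondary endpoint. A modest shift under a regimen could look somewhat smaller than it was at the scheduled draw.

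**Working it through.** The documents give no figure to reproduce. They state neither the fraction of results repeated nor the retest correlation, so what follows is an illustration under stated assumptions.

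**Inputs**
- From the documents: 16 subjects, each receiving all three regimens (Protocol 4); out-of-range trigger and last-value rule (Protocol 6.3.5).
- Assumed: normal values in units of the between-subject SD; upper reference limit L = 1.96 (97.5th percentile); every high value repeated once; retest correlation ρ from 0.6 to 0.9; no true change between tests.

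**Direction.** Only out-of-range values are retested. Each repeat is either still out of range or back in range, so the recorded out-of-range count cannot rise through this trigger.

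**Effect on the mean.** Let the first value be X ~ N(d, 1), where d is the shift. The repeat is Y = d + ρ(X − d) + error, with variance 1. Y is recorded if X > L, otherwise X. Then

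recorded mean = d − (1 − ρ) φ(L − d).

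- d = 1: φ(0.96) = 0.2516. Loss = 0.4 × 0.2516 = 0.101 (ρ = 0.6) to 0.1 × 0.2516 = 0.025 (ρ = 0.9). Recorded mean 0.90 to 0.98.
- d = 2: φ(−0.04) = 0.3986. Loss = 0.159 to 0.040. Recorded mean 1.84 to 1.96.
- If only half of the high values are repeated, the loss halves. For d = 1 the recorded mean is 0.95 to 0.99.
- With no shift and both tails repeated, the losses cancel and the mean is unbiased.

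**Effect on the median.** SAP 3.1 uses medians for non-normal variables, in a paragraph that speaks of baseline variables. If the same convention is used after treatment, solving the recorded distribution for its 50% point gives 0.95 to 1.00 for d = 1 and 1.73 to 1.86 for d = 2.

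**Against sampling error.** The standard error of a mean of 16 is 1/√16 = 0.25 SD. For a median it is about √(π/2) × 0.25 = 0.31 SD. The largest mean loss above is 0.16 SD and the largest median loss is 2 − 1.73 = 0.27 SD. Both are below one standard error.

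**If values are still rising.** Let the true level rise by δ before the repeat. The recorded mean becomes d + δ P(X > L) − (1 − ρ) φ(L − d). The loss is cancelled when δ = (1 − ρ) φ(L − d) / P(X > L).
- d = 1: P(X > L) = 0.1685, so δ = 0.60 (ρ = 0.6) to 0.15 (ρ = 0.9).
- d = 2: P(X > L) = 0.516, so δ = 0.31 to 0.08.
- With δ = 0.5 and d = 2, the recorded mean is 2.10 to 2.22, above the true value at the scheduled draw.

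**The case against.** The strongest reply is that abnormal results are captured elsewhere. Protocol 11.1 and 11.2 make them adverse events, the limits in 10.3 act on any single value, 12.5.2 requires values of concern to be described, and monitors see the source records. A reader might therefore infer from 6.3.5 that a safety signal would be lost. The documents do not support that: none of these routes depends on which value ends up in the laboratory fields of the CRF. There is one limit. For laboratory tests not in CTCAE, 11.4.1 leaves adverse event status to the investigator's judgement of clinical significance. What remains of the concern is that none of these routes puts the first value back into the laboratory dataset, so an event could be reported with no matching abnormal value in the summaries.

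A reader might also infer that the plan leaves open which value is recorded or summarised. It does not. The last-value rule is explicit, and the summaries would use what is recorded. The gap is narrower: what counts as a further result for the same time point.

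The size objection stands. The effect is small, rests on assumed inputs, takes full repetition as an extreme reading of a discretionary rule, and can change sign. Neither document plans a count of abnormal values, so a lower count matters only if one is produced.

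Repeating a doubtful result is also legitimate practice, and Protocol 6.1.2 relies on results reviewed before dosing. The fix must leave room for both.

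**Conclusion.** The concern holds as a minor point on data handling. Protocol 6.3.5 states a rule under which first abnormal values can be selectively replaced in the laboratory data that SAP 3.5.3 summarises, and it sets no time point for what counts as a repeat. That the out-of-range count cannot rise follows from the trigger alone.

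The size of any effect on means or medians depends on the normal model, the reference limit, the correlation, the repeat fraction and the absence of true change, none of which the documents supply. Within the ranges shown it is too small to be seen with 16 subjects, and it could run the other way. The text shows what could happen, not that it would be done or that the effect would differ between regimens. The primary pharmacokinetic analysis does not use these data.

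**What to change.** **Protocol 6.3.5.** Replace the last-value sentence with: all original and repeat results are recorded in the CRF with date and time, and repeats are flagged; a first value is excluded only for a documented sample or assay fault, such as haemolysis.

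**SAP 3.5.3.** Add three statements:
- post-dose laboratory summaries use the valid result from the scheduled draw;
- the pre-dose baseline is the last valid result before the first dose of each regimen;
- repeat and unscheduled values are listed.

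The separate baseline statement is needed because a repeat made before dosing is properly the pre-dose value, whereas a repeat made after dosing should not displace the scheduled one.

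The cost is a few sentences, a CRF page for repeats and a few more abnormal values to list. No extra tests are needed and no clinical rule changes.
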